3.1.2. Part B: Monotherapy Intensive Dosing

Part B will evaluate the safety and tolerability of SEA-BCMA dosed q1wk during an induction phase (for 8 doses during the first 2 cycles of therapy); following the completion of the 8 week induction phase, subjects who have not yet experienced confirmed disease progression may proceed to receive SEA-BCMA dosed q2wk during a maintenance phase (Cycle 3 and beyond, dosing at the recommended standard-schedule monotherapy expansion dose determined in Part A).

Part B will include a safety run-in at the recommended SEA-BCMA monotherapy expansion dose (1600 mg), administered on the intensive dosing schedule (Day 1, Day 8, Day 15, and Day 22 of Cycles 1 and 2, and Day 1 and Day 15 of subsequent cycles). DLTs will be evaluated in the first 6 subjects.

4. If 0 or 1 of the first 6 subjects experience DLT, the expansion cohort will proceed to enroll up to 20 total subjects with the recommendation of the SMC.
5. If ≥ 2 DLTs occur in the first 6 subjects, MTD will be considered exceeded and the dose of SEA-BCMA will be de-escalated to the next lower dose level (800 mg q1wk x 8 weeks during Cycles 1 and 2, followed by 1600 mg q2wk from Cycle 3 and beyond).
 - If 0 or 1 of the first 6 subjects at the lower dose level experience a DLT, the expansion cohort will proceed to enroll up to 20 total subjects at this dose level with the recommendation of the SMC.
 - If ≥ 2 DLTs occur in the first 6 subjects at the lower dose level, MTD will be considered exceeded, and the Part B Monotherapy Intensive Dosing cohort will be discontinued.

Subjects who are deemed not evaluable for DLT during dose finding will be replaced.

Table 4: Planned dose levels for Part B

Dose Level	Weekly Induction Dose, Cycles 1-2 (mg)	Biweekly Maintenance Dose, Cycles 3 and beyond (mg)
1	1600	1600
-1 (if Dose Level 1 is not tolerated)	800	1600

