3.1.5. Dose-Limiting Toxicity

The DLT-evaluation period is the first cycle of treatment. DLTs are graded according to the National Cancer Institute's Common Terminology Criteria for Adverse Events (NCI-CTCAE), version 4.03, and defined as any of the following events during the DLT-evaluation period:

- A delay of SEA-BCMA treatment by more than 7 days due to toxicity
- Any AE \geq Grade 3, unless deemed by the SMC to be clearly unrelated to SEA-BCMA (in Parts A through D) except for the following AEs, which must meet these specified criteria to be considered a DLT:
 - Grade 4 neutropenia lasting more than 5 days

- Thrombocytopenia \geq Grade 4, or Grade 3 thrombocytopenia with clinically significant bleeding
- Anemia \geq Grade 4 unrelated to underlying disease
- Any Grade ≥ 3 tumor lysis syndrome, including associated laboratory evaluations, that is not successfully managed clinically and that does not resolve within 7 days without end organ damage
- Any \geq Grade 4 IRRs or Grade 3 IRRs that do not resolve to \leq Grade 2 within 24 hours with infusion interruption, infusion rate reduction, and/or standard supportive measures. In the event of a Grade 3 IRR in $\geq 20\%$ of subjects (ie, 2 or more in the first 10 subjects), all subsequent subjects will require premedication and/or modification of infusion approach per the recommendation of the SMC. For subjects receiving premedication, any \geq Grade 3 IRR will be considered a DLT.
- Any Grade ≥ 3 asymptomatic laboratory abnormality that does not resolve, with or without intervention, to \leq Grade 1 or the baseline grade within 72 hours
- Any treatment-related death

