5.2.3. Dose Modifications

On a per-subject basis, lengthening of dosing intervals for toxicity, including DLT, may be allowed upon approval by the medical monitor. Subjects who experience DLT in Cycle 1 should not receive further treatment with SEA-BCMA unless clinical benefit is demonstrated with adequately managed toxicity and there is approval from the medical monitor. Examples of clinical benefit include an OR assessed by imaging, laboratory assessment, or physical examination; or SD and clinical improvement in disease-related symptoms per investigator. If clinical benefit is demonstrated, the dosing interval may be lengthened by 50 to 100% after discussion with the medical monitor. The type and severity of the AE observed will be taken into consideration to inform the decision. For subjects treated at the lowest dose level, the dosing interval may be lengthened, or the subject may be discontinued from treatment.

If a subject has a clinically significant, unresolved AE on the planned dosing day, the dose may be delayed for up to 7 days. Dosing delays due to other reasons or lasting >7 days must be discussed with the medical monitor (see [Table 5](#)); during the DLT period, subjects should not receive further treatment with SEA-BCMA unless clinical benefit is demonstrated with adequately managed toxicity and there is approval from the medical monitor. For subjects requiring a dose delay >7 days due to an unresolved AE, the dosing interval may be lengthened by 50 to 100% after discussion with the medical monitor.

In q2wk dosing, if a subject has a clinically significant, unresolved AE on Day 15 that prevents dosing, the Day 15 visit may be delayed for ≤ 7 days. On the seventh day, if a subject cannot receive the dose, the second dose of the cycle will be eliminated, the Day 15 visit will be skipped, and the Day 22 visit will be performed. If the Day 15 dose is delayed for ≤ 7 days, study assessments required for Day 15 to 28 will be delayed by the same number of days as the dose delay, and study drug administration for the next cycle will be delayed by at least the same number of days.

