In intensive dosing weekly induction Cycles 1 and 2, if a subject has a clinically significant, unresolved AE that prevents dosing on Day 8, 15, or 22, the dose may be delayed for ≤ 3 days. On the third day, if a subject cannot receive the dose, the dose of SEA-BCMA will be eliminated and the corresponding visit will be skipped; dosing and visit schedule would resume the following week (eg, at Day 22, if Day 15 is skipped). However, if a Day 8, 15, or 22 dose is delayed for ≤ 3 days, subsequent study assessments within the same cycle will be delayed by the same number of days as the dose delay, and study drug administration for the next dose will be delayed by at least the same number of days.

During the DLT period (Cycle 1), growth factor and transfusion support is discouraged unless medically indicated; subjects who receive growth factor (eg, granulocyte colony-stimulating factor or granulocyte-macrophage colony-stimulating factor) or transfusion support (other than

red blood cell transfusions for MM-related anemia) during this period for reasons other than DLT may not be evaluable for DLT, except in Part D, where granulocyte colony-stimulating factor is permitted during Cycle 1 if given as primary or secondary prophylaxis in conjunction with pomalidomide. Consideration should be given for growth factor support for prophylaxis or treatment of cytopenias in subsequent cycles (Table 5). During dose-escalation, subjects with Grade 4 neutropenia must have a follow-up complete blood count (CBC) with differential obtained 5 days from the time of assessment for evaluation of DLT. In addition, subjects with Grade 3 asymptomatic laboratory abnormalities must have follow-up laboratory evaluation obtained 72 hours from the time of assessment for evaluation of DLT. Serum chemistry and CBCs should be collected minimally on a weekly schedule during dose delays resulting from toxicity.

Table 5 describes the recommended dose modifications for toxicity.

Table 5: Recommended dose modifications for toxicity

Toxicity	Grade 1	Grade 2	Grade 3	Grade 4
Nonhematologic (AE or laboratory abnormality)	Continue at same dose level	Continue at same dose level	Withhold dose until toxicity is \leq Grade 1 or baseline ^a , and then resume treatment at 50% of the SEA-BCMA dose	Discontinue study treatment

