9.3.1.7.3. DLT-Evaluable Analysis Set

The DE Analysis Set includes All Treated Subjects who either experienced a DLT, or were followed for the full DLT evaluation period and received a minimum 75% of the intended total Cycle 1 SEA-BCMA dose, and did not receive prohibited treatment (see Section 5.6.2 and Section 5.6.3). The DE analysis set will be used for determination of the MTD.

Additional details of analyses and analysis sets of subjects may be defined in the SAP.

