4.2 DLT Evaluatable (DE) Analysis Set

The DLT-evaluative (DE) analysis set will include all treated patients who either (1) experience a DLT, or (2) receive at least 75% of the intended SEA-BCMA dose and are followed for the full DLT evaluation period. The DLT evaluation period is defined as cycle 1 of treatment. For q2wk schedule, cycle 1 includes the first 2 doses of treatment. Patients will be replaced for DLT evaluation if they received prohibited medications (as described in protocol Sections 5.4.2 and 5.4.3), or are deemed inevaluable for clinical reasons by the SMC. Patients on the q2wk dosing schedule who receive only the 1st dose during cycle 1 for reasons other than toxicity may not be DLT-evaluative and will be replaced.

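### On weekly dosing, toxicity short of a DLT can drop a subject below the 75% dose threshold and lead to replacement, so evaluability for the run-in decision depends on tolerability

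*Protocol*

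**What the plan says.** **Evaluability.** Protocol 9.3.1.7.3: "The DE Analysis Set includes All Treated Subjects who either experienced a DLT". A subject without a DLT must have been followed for the whole period, have "received a minimum 75% of the intended total Cycle 1 SEA-BCMA dose", and have had no prohibited treatment. The reason for a dose shortfall plays no part. The definition in the protocol synopsis has no 75% condition.

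**Replacement and decision.** Protocol 3.1.2 (Part B): "Subjects who are deemed not evaluable for DLT during dose finding will be replaced". Section 3.1.3.2 (Part C) has the same rule. The Part B decision is: "If 0 or 1 of the first 6 subjects experience DLT, the expansion cohort will proceed". Two or more DLTs mean that the MTD is exceeded. Part C applies the same six-subject limits.

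**Delay as a DLT.** Protocol 3.1.5 includes: "A delay of SEA-BCMA treatment by more than 7 days due to toxicity".

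**Missed doses.** Protocol 5.2.3, weekly induction: "On the third day, if a subject cannot receive the dose, the dose of SEA-BCMA will be eliminated", with dosing resumed the following week. For q2wk, if Day 15 cannot be given by the seventh day, "the second dose of the cycle will be eliminated".

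**SAP 4.2.** It repeats the 75% condition without a toxicity exception. It then says that q2wk patients "who receive only the 1st dose during cycle 1 for reasons other than toxicity" may not be evaluable and will be replaced. The weekly schedule has no such sentence.

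**The concern.** A run-in asks whether a dose is tolerable. If a subject can leave the denominator because the dose was poorly tolerated, but not badly enough to meet a DLT criterion, then the six subjects who decide the question have been selected partly on the answer. Each subject is one sixth of the evidence, and the boundary lies between one DLT and two, so the handling of a single subject can reverse the decision. No planned display would show this. Protocol 9.3.9.3 and SAP 5.1 and 6.6.2 report DLT proportions for dose escalation only.

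**Working it through.** The documents give no operating characteristics for the six-subject run-ins, so there is no stated figure to reproduce.

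**Step 1: which patterns fall below 75%.** Share = doses received / doses planned in Cycle 1. Lateness = next dose given minus the planned day of the missed dose, on nominal days and ignoring the visit windows.

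| Schedule and pattern | Share of Cycle 1 dose | Lateness | Status without another DLT |
|---|---|---|---|
| Weekly, one dose eliminated | 3/4 = 75% | 7 days | stays in |
| Weekly, two half doses | (2 + 2 × 0.5)/4 = 75% | none | stays in |
| Weekly, Days 8 and 22 eliminated | 2/4 = 50% | 15 − 8 = 7 and 29 − 22 = 7 days | out, replaced |
| Weekly, half doses on Days 8, 15 and 22 | (1 + 3 × 0.5)/4 = 62.5% | none | out, replaced |
| Weekly, one eliminated and one half dose | (2 + 0.5)/4 = 62.5% | 7 days | out, replaced |
| Weekly, Days 8 and 15 eliminated | 2/4 = 50% | 22 − 8 = 14 days | depends on whether elimination counts as delay |
| q2wk, Day 15 at half dose | 1.5/2 = 75% | none | stays in |
| q2wk, Day 15 eliminated | 1/2 = 50% | 29 − 15 = 14 days | depends on whether elimination counts as delay |

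**Step 2: whether non-DLT toxicity can produce them.** Two routes follow from the protocol.
- Section 3.1.5 excepts Grade 3 neutropenia and Grade 3 anemia from the DLT definition. Table 5 in 5.2.3 withholds the dose for them. Repeated withholding can give the Days 8 and 22 pattern, and neither gap exceeds 7 days.
- Section 3.1.5 also excepts an asymptomatic Grade 3 laboratory abnormality that resolves within 72 hours. For a nonhematologic one, Table 5 resumes dosing at 50%. If this follows Day 1 and the reduction lasts through Day 22, the share is 62.5%.

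**Step 3: effect on the decision.** Let d be the DLT rate as defined, among all treated subjects, and t the share below 75% because of toxicity without a DLT. Both values are assumptions. The DLT rate per subject counted is:
- kept as non-DLT: d
- excluded and replaced: d/(1 − t)
- counted as events: d + t

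P(pass) = (1 − p)^6 + 6p(1 − p)^5. With d = 0.20 and t = 0.10:
- p = 0.20: 0.262 + 0.393 = 0.655
- p = 0.20/0.90 = 0.222: 0.221 + 0.380 = 0.601
- p = 0.30: 0.118 + 0.303 = 0.420

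| d | t | kept as non-DLT | replaced | counted as events |
|---|---|---|---|---|
| 20% | 5% | 0.655 | 0.630 | 0.534 |
| 20% | 10% | 0.655 | 0.601 | 0.420 |
| 20% | 15% | 0.655 | 0.569 | 0.319 |
| 25% (Part A target rate) | 10% | 0.534 | 0.469 | 0.319 |

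**Step 4: direction.** Everyone excluded under the 75% rule has no DLT, so d/(1 − t) is above d. It is below d + t in every row. Suppose a fraction h of those excluded would have had a DLT with full dosing. The rate to compare with is then d + t·h, and the observed rate is too low only if h exceeds d/(1 − t), which is 22.2% at d = 20% and t = 10%.

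**The case against.** The strongest reply concerns direction. A reader might infer that replacement biases the run-in DLT rate downward. Against the DLT rate as the protocol defines it, Step 4 shows the opposite: replacement raises the observed rate and makes the run-in harder to pass (0.601 against 0.655). It is too low only against a broader tolerability rate, or if h is above the break-even value, and the documents show neither. This stands, and no downward bias is claimed here.

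Second, q2wk may already be covered. If an eliminated Day 15 dose counts as a delay of more than 7 days, the subject has a DLT and stays in, and the SAP's toxicity wording is then consistent with its 75% condition. That is a fair reading. The text does not settle it, so q2wk is an ambiguity and not a demonstrated gap.

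Third, the gap is narrow. One missed weekly dose or two half doses stay in at exactly 75%, and most Grade 3 or higher events are DLTs anyway. A reader might also expect recurrent Grade 2 infusion reactions to create cases. Under Table 8, dose reduction is considered only after recurrence despite added measures. With a first reaction on Day 1, the earliest half dose is Day 15, giving (1 + 1 + 0.5 + 0.5)/4 = 75%, and the subject stays in. The narrowness stands; the patterns in Step 1 remain.

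Fourth, the SMC reviews the run-in data and must recommend expansion, and SAP 6.6.1 tabulates events leading to dose elimination, delay or reduction in all treated patients. These make the toxicity visible. They do not change who is counted in the six.

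**Conclusion.** On the weekly schedule, the protocol removes and replaces some subjects because of toxicity that is not a DLT, so evaluability depends on tolerability. On q2wk, the documents leave open whether an eliminated dose is a delay DLT. At an assumed d = 20% and t = 5% to 15%, the chance of passing runs from 0.63 to 0.57 if such subjects are replaced, against 0.655 if they are kept as non-DLT and 0.53 to 0.32 if they are counted as events. The share t and the fraction h are not in the documents, so the size is illustrative and the direction depends on the comparator. The effect is on a go/no-go decision, because no run-in DLT rate is planned for reporting. The point deserves correction because one subject can move the result across the boundary and the remedy is cheap.

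**What to change.** - In protocol 9.3.1.7.3 and SAP 4.2, limit replacement for a dose shortfall to reasons other than toxicity on every schedule. This extends what SAP 4.2 already says for q2wk.
- Have the SMC classify each toxicity-driven shortfall, and record the classification, before any replacement.
- List all replaced run-in subjects with reasons. Show the run-in DLT count with toxicity-shortfall subjects excluded, kept as non-DLT, and counted as events.
- Reconcile the protocol synopsis, 3.1.5, 5.2.3, 9.3.1.7.3 and SAP 4.2 on whether an eliminated dose counts as a delay and whether the 75% condition applies. Which dosing or DLT rule is right is for the sponsor and the SMC.

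The cost is minor wording and one extra display. A run-in may look more favourable where these subjects are kept as non-DLT, or less favourable where the SMC classifies them as DLTs. If the run-ins are already complete, the listing and the three-way count can still be produced for the study report.

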9.3.1.8. Examination of Subgroups

All analyses will be presented by dose level and total. Details will be defined in the SAP.

As exploratory analyses, subgroup analyses may be conducted for selected endpoints. Subgroups may include but are not limited to the following:

- Age (<65 vs \geq 65 years old)
- Cytogenetic risk group (high, intermediate, normal)
- Refractory to prior therapies (refractory to IMiDs and PIs vs not)
- Number of prior therapies (<5 vs \geq 5)
- Baseline beta-2 microglobulin (<3.5 vs \geq 3.5)

- BCMA expression levels

Detailed methodology will be provided in the SAP.

9.3.1.9. Timing of Analyses

The final analysis for this study will occur after all subjects have completed their treatment and the follow-up period or following study termination by the sponsor.

For timing of interim analysis, see Section [9.3.10](#).

9.3.2. Subject Disposition

An accounting of study subjects by disposition will be tabulated and the number of subjects in each analysis set will be summarized. Subjects who discontinue study treatment and subjects who withdraw from the study will be summarized with reason for discontinuation or withdrawal.

9.3.3. Subject Characteristics

Demographics and other baseline characteristics will be summarized. Details will be provided in the SAP.

9.3.4. Treatment Compliance

The dose administered at each cycle, dose intensity, and dose modifications will be summarized. Details will be provided in the SAP.

9.3.5. Efficacy Analyses

All efficacy analyses will be presented using the All Treated Subjects set. Selected efficacy endpoints will also be presented using the efficacy-evaluable analysis set. The observed ORR and CR rate and corresponding 95% CIs will be presented. Subjects whose disease response cannot be assessed will be counted as non-responders. Subjects with intrasubject dose-escalation prior to achieving a response will be counted as non-responders at their initial dose.

Duration of response, PFS and OS will be estimated using Kaplan-Meier methodology, and Kaplan-Meier plots will be provided. Medians will be calculated, where possible. The 95% CIs may also be calculated, as appropriate.

Detailed methodology will be provided in the SAP.

9.3.6. Pharmacokinetic and Immunogenicity Analyses

The PK of SEA-BCMA will be evaluated by noncompartmental analysis. The following PK parameters will be determined where data allow:

- Area under the curve
- Concentration at the end of infusion (C_{eoI}) or C_{max}
- Trough concentration (C_{trough})
- Terminal or apparent terminal half-life ($t_{1/2}$)
- Systemic clearance and volume of distribution at steady state

- Accumulation ratio

The incidence of ATA will be summarized by descriptive statistics.

9.3.7. Qualitative Interview Analyses

No formal statistical analysis will be performed on the qualitative interviews.

9.3.8. Biomarker Analyses

Peripheral blood and BM aspirates and biopsies will be collected for biomarker assessments. Assessments performed with these samples may include, but are not limited to, myeloma cell monitoring and profiling, including expression of BCMA and assessments of immune cell populations. Additionally, BM samples may be analyzed to identify gene expression profiles, cytogenetic abnormalities, genetic mutations, and other tumor and tumor microenvironment-related biomarkers that may define disease risk profiles, predict response to SEA-BCMA, and clarify SEA-BCMA mechanisms of action. MRD will be analyzed in selected BM specimens using NGS. Plasma and serum will also be collected for quantification of biomarkers of drug activity, which may include SFLC, cytokines/chemokines, soluble BCMA, and other soluble biomarkers.

Relationships of biomarker and pharmacodynamic parameters (eg, baseline values, absolute and relative changes from baseline) to efficacy, safety and PK parameters will be explored.

Relationships and associated data that are determined to be of interest will be summarized. These exploratory analyses will be described in a separate analysis plan (eg, the SAP or Biomarker Analysis Plan); clinically relevant findings may be described in the clinical study report or reported separately (eg, in an Exploratory Studies Report).

9.3.9. Safety Analyses

9.3.9.1. Extent of Exposure

Duration of treatment will be summarized and listed.

Duration of treatment, number of cycles, total dose and dose intensity will be summarized. Dose modifications will also be summarized. Details will be provided in the SAP.

9.3.9.2. Adverse Events

An overview of AEs will provide a tabulation of the incidence of all AEs, treatment-emergent AEs, treatment-related AEs, Grade 3 and higher AEs, SAEs, treatment-related SAEs, deaths, AEs leading to study treatment discontinuation, treatment-related TEAEs leading to study treatment discontinuation, TEAEs and treatment-related TEAEs leading to dose reduction and interruption. AEs will be defined as treatment-emergent if they are newly occurring or worsen following study treatment.

AEs will be listed and summarized by Medical Dictionary for Regulatory Activities (MedDRA), preferred term, SOC, severity, and relationship to study drug. In the event of multiple occurrences of the same AE with the same preferred term in 1 subject, the AE will be counted once as the occurrence. The incidence of AEs will be tabulated by preferred term and treatment

group. AEs leading to premature discontinuation of study drug will be summarized and listed in the same manner.

9.3.9.3. Dose-Limiting Toxicity

The observed number and proportion of subjects experiencing a DLT will be reported for the dose-escalation part.

9.3.9.4. Deaths and Serious Adverse Events

All SAEs will be listed and summarized in the same manner as all AEs. Events with a fatal outcome will be listed.

9.3.9.5. Clinical Laboratory Results

Laboratory values (eg, chemistry, hematology, urinalysis, and pulmonary function tests) may be presented graphically by visit. Summary statistics may be tabulated as appropriate by scheduled visit. Laboratory values will be listed with grade per NCI-CTCAE v. 4.03 and flagged when values are outside the normal reference range.

